Attachment 2. Protocol JGDN Clinical Laboratory Tests

Clinical Laboratory Tests

Hematology^a	Clinical Chemistry^a
Hemoglobin	Serum Concentrations of the following:
Hematocrit	Sodium
Erythrocyte count (RBC)	Potassium
Mean cell volume (MCV)	Total bilirubin
Mean cell hemoglobin concentration (MCHC)	Alkaline phosphatase
Leukocytes (WBC)	Alanine aminotransferase (ALT)
Neutrophils	Aspartate aminotransferase (AST)
Lymphocytes	Gamma glutamyl transferase (GGT)
Monocytes	Blood urea nitrogen (BUN) or Blood Urea
Eosinophils	Creatinine
Basophils	Urate
Platelets	Calcium
	Glucose, random
	Albumin
	Total protein
	Chloride
	Thyroid-stimulating hormone
	Direct bilirubin
	Bicarbonate
	Magnesium
	Phosphate
Coagulation Test^a	
Prothrombin time (PT)	
International normalized ratio (INR)	
Partial thromboplastin time (PTT or aPTT)	
Urinalysis^{a,c}	
Specific gravity	
pH	
Protein	
Glucose	
Ketones	
Blood	
Urine leukocyte esterase	
Other^b	
Immunogenicity samples	
PK samples	
Pregnancy test^{a,d}	
Exploratory Biomarker Tests^b	

Abbreviations: CRP = clinical research physician; PK = pharmacokinetics; RBC = red blood cells; UPC = urine protein/creatinine; WBC = white blood cells.

a Assayed by local or investigator-designated laboratory.

b Samples will be assayed by Lilly-designated laboratory.

c If urinary protein is $\geq 2+$ at evaluations, a 24-hour urine collection (to assess protein) must be collected and must be ≤ 1000 mg of protein in 24 hours, or alternatively, a urine protein/creatinine ratio ≤ 1 , prior to proceeding to the next cycle. Note: UPC ratio of spot urine is an estimation of the 24-hour urine protein excretion – a UPC ratio of 1 is roughly equivalent to a 24-hour urine protein of 1000 mg. UPC ratio is calculated using one of the following formulae:

- $[\text{urine protein}]/[\text{urine creatinine}]$ – if both protein and creatinine are reported in mg/dL
- $[(\text{urine protein}) \times 0.088]/[\text{urine creatinine}]$ – if urine creatinine is reported in mmol/L

d Serum pregnancy test will be performed at screening in female patients of childbearing potential only (if the baseline serum test is positive, a repeat serum and urine pregnancy test will be done; if those results are positive, the investigator is to consult with the Lilly CRP regarding if dosing should occur and which follow-up laboratory tests are performed). While on-study, urine pregnancy test will be performed in female patients of childbearing potential only on Day 1 of every cycle or per local practice (whichever is of shorter duration) and at short-term follow-up visit. If the serum pregnancy test performed for inclusion purposes is positive confirm by repeating the serum and performing a urine pregnancy test. If the urine pregnancy test performed on Day 1 of each cycle is positive, confirm with a serum pregnancy test.

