Altogether, preclinical and clinical data support exploring olaratumab in combination with standard chemotherapy regimens for patients with sarcomas and other pediatric tumors. The present Phase 1 study (JGDN) has been developed based on regulatory input and advice from external experts, who recommended minimizing the exposure to single-agent therapy in pediatrics prior to continuing on standard combination chemotherapy regimens commonly used for specific tumor subtypes. In this regard, the proposed study intends to enroll pediatric patients aged from 0 to less than 18 years of age with solid tumors for 1 cycle of olaratumab monotherapy and subsequently move to standard therapies with either doxorubicin, or vincristine/irinotecan, or high-dose ifosfamide. Olaratumab monotherapy will start at 15 mg/kg, a dose which was efficacious in adults (Study JGDG). A dose of 15 mg/kg olaratumab is expected to achieve a similar serum exposure level in both the pediatric and adult populations (see Section 5.4). Furthermore, in 2 previous Phase 1 dose-escalation trials (I5B-IE-JGDC [JGDC] and I5B-IE-JGDF [JGDF]) and in the 2 Phase 2 monotherapy studies (I5B-IE-JGDE [JGDE] and I5B-IE-JGDH [JGDH]) in adults, single-agent olaratumab has consistently been well tolerated, with no dose-limiting toxicities (DLTs) observed up to a dose of 16 mg/kg weekly times 4 doses in a 6 week cycle, 20 mg/kg administered every 2 weeks, and up to a dose of 15 mg/kg administered of Day 1 and Day 8 of a 21-day cycle.

The primary objective in Study JGDN will be to assess the safety profile of olaratumab as a single agent and in combination with either doxorubicin, vincristine/irinotecan, or high-dose ifosfamide. The secondary objectives will include the pharmacokinetic (PK) profile of olaratumab as a single agent and in combination with doxorubicin, vincristine/irinotecan, or high-dose ifosfamide and the antitumor activity of the combination chemotherapies. These regimens are recommended according to standard clinical practice in pediatric patients (Sandler et al. 2001; Carli et al. 2003; Mascarenhas et al. 2010).

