- Serum creatinine is based on age/gender as follows:

Age	Maximum Serum Creatinine (mg/dL)	
	Male	Female
1 month to < 6 months	0.4	0.4
6 months to < 1 year	0.5	0.5
1 to < 2 years	0.6	0.6
2 to < 6 years	0.8	0.8
6 to < 10 years	1.0	1.0
10 to < 13 years	1.2	1.2
13 to < 16 years	1.5	1.4
$\geq 16 \text{ years}$	1.7	1.4

The threshold creatinine values in this table were derived from the Schwartz formula for estimating glomerular filtration rate ([Attachment 6](#)).

- The patient has an adequate coagulation function as defined by International Normalized Ratio ≤ 1.5 or prothrombin time $\leq 1.5 \times$ ULN, and partial thromboplastin time $\leq 1.5 \times$ ULN if not receiving anticoagulation therapy. For patients receiving anticoagulants, exceptions to these coagulation parameters are allowed if they are within the intended or expected range for their therapeutic use. Patients must have no history of active bleeding (defined as within 14 days of first dose of study drug) or pathological condition that carries a high risk of bleeding (for example, tumor involving major vessels or known esophageal varices).

[7] Female patients of child-bearing potential must have a negative serum pregnancy test within 7 days prior to Cycle 1 Day 1.

- [8] Both female and male patients of child-bearing potential must agree to use highly effective contraceptive precautions during the trial and up to 3 months following the last dose of olaratumab, or longer if appropriate for other study drugs according to their label. A highly effective method of birth control is defined as one that results in a low failure rate (that is, <1% per year) when used consistently and correctly, such as implants, injectables, combined oral contraceptives, some intrauterine contraceptive devices, sexual abstinence, or a vasectomized partner.
- [9] Patients must have fully recovered from the acute toxic effects of all prior anticancer therapies or must adhere to post-treatment conditions as follows:
 - Myelosuppressive chemotherapy: at least 21 days after the last dose of myelosuppressive chemotherapy (or 42 days if prior nitrosourea)

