Attachment 1. Protocol JGDN Study Schedule

JGDN Study Schedule, Screening and Baseline Assessments (All Parts)

Relative Day Prior to Cycle 1 Day 1	≤28	≤14	≤7	Comments
Eligibility Assessments				
Informed Consent				
Informed Consent	X			Written informed consent must be obtained prior to any study-specific screening evaluations.
Medical History		X		
Lansky/Karnofsky performance status		X		To be assessed by the investigator.
ECG	X			Consecutive replicate ECGs (3 readings) will be obtained, whenever feasible for the patient, at approximately 1-minute intervals.
ECHO or MUGA	X			For patients that will receive doxorubicin, ECHO or MUGA must be performed within 28 days prior to C1D1.
Safety Assessments				
Physical Exam		X		Physical exam includes height, weight, and BSA measurement.
Vital Signs		X		Vital sign measurements include temperature, pulse rate, and blood pressure.
Concomitant Medication Assessment		X		Concomitant medications will be recorded including any taken within 30 days prior to study medication.
Laboratory Assessments (See Attachment 2 for details)				
Hematology Profile		X		Screening evaluations done within 7 days prior to C1D1 do not have to be repeated unless otherwise specified.
Coagulation Profile		X		
Chemistry Profile		X		
Urinalysis			X	Includes a routine urinalysis, and if clinically indicated, a microscopic analysis. If routine analysis indicates > 2+ proteinuria, then a 24-hour urine must be collected and must demonstrate ≤ 1000 mg of protein in 24 hours, or urine protein/creatinine ratio < 1, prior to proceeding to treatment. Screening evaluations done within 7 days prior to C1D1 do not have to be repeated unless otherwise specified.
Pregnancy Test			X	Serum β-HCG pregnancy test (women of childbearing potential only) within 7 days prior to C1D1. If the serum pregnancy test performed for inclusion purposes is positive, confirm by repeating the serum and performing a urine pregnancy test.
Genetic (whole blood) Sample		X		See Section 8.2.3 (whole blood sample).

Relative Day Prior to Cycle 1 Day 1	≤ 28	≤ 14	≤ 7	Comments
Efficacy Assessments				
Imaging Studies (CT/MRI/chest x-ray)	X			For rapidly growing tumors, scans should be performed ≤ 14 days prior to C1D1. Scans performed prior to the date of consent may be used provided they are within 28 days of C1D1. RECIST v1.1 should be used for all tumors with the exception of CNS tumors; RANO or Macdonald criteria should be used for CNS tumors.

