Attachment 5. Protocol JGDN Recommendations for Reporting Serious Adverse Events

Recommendations for Reporting Serious Adverse Events

When contacting Lilly to report a SAE, please have the following information available:

Patient Demographics

- patient identification (number), sex, date of birth, origin, height, and weight

Study Identification

- full trial protocol number, investigator's name, investigator's number

Study Drug

- drug code or drug name, unit dose, total daily dose, frequency, route, start dose, cycle details, start date and last dose date (if applicable)

Adverse Event

- description, date of onset, severity, treatment (including hospitalization), action taken with respect to study drug, clinical significance, test and procedure results (if applicable)

Relationship to Study Drug & Protocol Procedures

Concomitant Drug Therapy

- indication, total daily dose, duration of treatment, start date, action taken

In Case of Death

- cause, autopsy finding (if available), date, relationship to study drug and protocol procedures.

**Attachment 6. Protocol JGDN Creatinine Clearance
Formula**

Protocol JGDN will use the Schwartz formula for the determination of creatinine clearance.

All Females and Pre-adolescent Males:

$$C_{cr} \text{ (mL/min/1.73 m}^2\text{)} = 0.55 \times \text{Height (cm)}/S_{cr} \text{ (mg/dL)}$$

Adolescent Males:

$$C_{cr} \text{ (mL/min/1.73 m}^2\text{)} = 0.70 \times \text{Height (cm)}/S_{cr} \text{ (mg/dL)}$$

Note: C_{cr} = creatinine clearance and S_{cr} = serum creatinine

Source: Schwartz et al. 1976; Schwartz and Gauthier 1985.

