#### Doxorubicin:

- Duration of treatment (weeks) = ([Date of last dose – date of first dose] + 21) ÷ 7
- Cumulative dose (mg) = Sum of all doses
- Cumulative dose level (mg/m^2) = Sum of (dose administered at each infusion [mg] ÷ Last available body surface area [BSA] [m^2] prior to that infusion)
- BSA (m^2) = 0.007184 \* weight (kg) ^0.425 \* height (cm) ^0.725

- Weekly dose intensity (mg/m^2/week) = (Cumulative dose level) ÷ (Duration of treatment)
- Planned weekly dose intensity (mg/m^2/week) = 2 x 37.5 mg/m^2/ 3 weeks=25
- Relative dose intensity (%)=(Weekly dose intensity) ÷ (Planned weekly dose intensity) x 100

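### The proteinuria rule treats 1000 mg/24 h and a urine protein/creatinine ratio of 1 as equivalent with no body-size qualification, so the same small child can pass one route and fail the other.

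*Protocol*

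**What the plan says.** Protocol Attachment 2, note c, applies once urinary protein reaches 2+ on routine testing. Before the next cycle the patient must then show at most "1000 mg of protein in 24 hours, or alternatively, a urine protein/creatinine ratio" of at most 1. The note justifies the pairing by saying that "a UPC ratio of 1 is roughly equivalent to a 24-hour urine protein of 1000 mg". It gives no age, weight or body surface area range for that statement.

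The screening table in Attachment 1 carries the same rule before first treatment: "a 24-hour urine must be collected and must demonstrate ≤ 1000 mg of protein in 24 hours, or urine protein/creatinine ratio < 1". The urinalysis rows of all six treatment schedules repeat it before each next cycle.

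Section 5.1 describes the population as "pediatric patients aged from 0 to less than 18 years of age". Very small patients are foreseen elsewhere: the serum creatinine table in Section 6.1.1 starts at 1 month, Table JGDN.7.1 has a separate vincristine dose below 10 kg, and Attachment 4 reduces PK blood volumes below 19 kg.

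Attachment 6 states that "Protocol JGDN will use the Schwartz formula for the determination of creatinine clearance", and Section 6.1.1 says of its eligibility limits that "The threshold creatinine values in this table were derived from the Schwartz formula". No passage scales the 1000 mg limit to body size or says which route prevails when they disagree.

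**The concern.** A UPC is protein divided by creatinine in the same urine. A ratio of 1 therefore matches 1000 mg of protein per day only in a patient who excretes about 1000 mg of creatinine per day. Creatinine excretion rises with body size, so one fixed pairing cannot hold from infancy to late adolescence.

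The two limits are joined by an either/or. If they diverge, the test a site happens to order decides whether a given child is treated or held. The rule applies at entry and before later cycles. It also covers the ifosfamide arm, where Section 7.2.4.5.2 names age under 5 years as a risk factor for nephrotoxicity and proteinuria as a feature of tubular damage.

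**Working it through.** **Inputs.** Schwartz clearance (Attachment 6): k × height / serum creatinine, in mL/min/1.73 m², with k = 0.55 for all females and pre-adolescent males and 0.70 for adolescent males. Body surface area (SAP Section 5.9.1): BSA = 0.007184 × weight^0.425 × height^0.725. Heights and weights are assumptions, because the documents project no size distribution.

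**Formula.** At steady state, daily creatinine excretion equals clearance × serum creatinine. Removing the 1.73 m² indexing and converting units (1440 min/day, 100 mL/dL), serum creatinine cancels:

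excretion (mg/day) = k × height × 14.4 × BSA / 1.73

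The multiplier k × 14.4 is 0.55 × 14.4 = 7.92, or 0.70 × 14.4 = 10.08. The UPC that corresponds to 1000 mg/24 h is 1000 / excretion.

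**Where the protocol's statement reproduces.** At 40 kg/150 cm, k = 0.55: BSA 1.303 m², excretion 7.92 × 150 × 1.303 / 1.73 = 895 mg/day, so 1000 mg is a UPC of 1.12. At 48 kg/157 cm: 1046 mg/day, UPC 0.96.

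**Across the enrolled range.**

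| Assumed size | k | BSA (m²) | Creatinine (mg/day) | UPC at 1000 mg/24 h |
|---|---|---|---|---|
| 4.5 kg, 55 cm | 0.55 | 0.249 | 63 | 16 |
| 10 kg, 75 cm | 0.55 | 0.437 | 150 | 6.7 |
| 14 kg, 95 cm | 0.55 | 0.599 | 260 | 3.8 |
| 19 kg, 112 cm | 0.55 | 0.768 | 394 | 2.5 |
| 32 kg, 140 cm | 0.55 | 1.127 | 722 | 1.4 |
| 54 kg, 162 cm (girl) | 0.55 | 1.565 | 1161 | 0.86 |
| 64 kg, 174 cm (adolescent boy) | 0.70 | 1.772 | 1796 | 0.56 |

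**Opposite decisions for the same urine.** A 10-kg, 75-cm child with 900 mg/24 h is within the 24-hour limit, but the UPC is 900 / 150 = 6.0, outside the ratio limit. The 64-kg boy with 1200 mg/24 h is outside the 24-hour limit, but the UPC is 1200 / 1796 = 0.67, within the ratio limit.

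**Sensitivity.** Giving the 10-kg child the larger coefficient of 0.70 raises excretion to 191 mg/day, and 1000 mg is still a UPC of 5.2. For a 12-kg, 85-cm child (201 mg/day) to fit the stated equivalence, k would have to be 0.55 × 1000 / 201 = 2.7.

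The 0.088 unit factor in note c is not at fault: 1 / 11.31 = 0.088.

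**The case against.** **A separate gate exists.** Section 7.2.4 requires any nonhematologic toxicity to be below CTCAE v4.0 Grade 2, or no worse than at baseline, before dosing at each cycle. Section 8.1.2 grades all adverse events by CTCAE v4.0, so proteinuria recorded as an adverse event faces this gate whichever urine test was used. A reader might infer from the table that the proteinuria safeguard is defeated in toddlers. The documents do not support that. They do not reproduce the CTCAE proteinuria grades, so how far this criterion closes the gap cannot be determined from them. It does not remove the mismatch: it depends on the finding being recorded and graded, and proteinuria already present at baseline may meet the baseline clause. The dose-limiting-toxicity definition, the olaratumab toxicity rules and the ifosfamide reductions are further protections, but none of them reconciles the two limits.

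**The conflict is derived.** Attachment 6 gives the Schwartz formula only for creatinine clearance, and the SAP uses its BSA formula for dose intensity. Neither states a creatinine excretion. The result needs the steady-state identity and assumed sizes. It is therefore an unqualified approximation that fails outside a size range, not two sentences in open contradiction. This stands and limits how strongly the point may be put.

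**The note says only roughly.** At 32 to 54 kg with k = 0.55 the corresponding UPC is 1.4 to 0.86, which that word can cover. It cannot cover 2.5 to 16. The figure of 16 rests on one assumed 4.5-kg infant, close to the youngest age in the eligibility table.

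**Few patients may be affected.** The limits apply only after a dipstick trigger, and the documents do not project how many patients will be small. This stands.

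**Conclusion.** The point holds in a bounded form. The stated equivalence is unqualified, and by the protocol's own clearance formula it is roughly right only at about 32 to 54 kg with k = 0.55. For the assumed sizes of 19 kg and below, the two limits differ about 2.5- to 16-fold, with the 24-hour route the more permissive. In a 64-kg adolescent boy the gap reverses, with 1000 mg at a UPC of about 0.56. Either route suffices after the trigger, so the same child can pass one and fail the other.

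This rests on steady-state creatinine, the Schwartz and SAP formulas, and assumed heights and weights; it does not depend on serum creatinine. A reader might also infer that the ratio limit is the right one and the 24-hour limit the error. The documents do not say which governs, and the calculation shows only that the two disagree. No endpoint, analysis set or escalation rule uses this limit. The matter is one of patient safety and consistent conduct, and should be corrected.

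**What to change.** Remove the equivalence statement from Attachment 2 note c, or qualify it by body size. Reconcile note c, the urinalysis rows of Attachment 1 (screening and all six treatment schedules) and the cycle-start criterion in Section 7.2.4, so that the routes give the same decision in the same child at every enrolled body size and the text says how they relate. The same edit can align two smaller differences: the trigger (2+ or more in note c, above 2+ in the schedules) and the ratio limit (at most 1 in note c, below 1 in the schedules). Which limit or route applies is for the sponsor's clinical team.

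The cost is protocol wording only. Some patients' proceed or hold decisions may change.

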Attachment 3. Protocol JGDN Hepatic Monitoring Tests for Treatment Emergent Abnormality

Selected tests may be obtained in the event of a treatment emergent hepatic abnormality and may be required in follow up with patients in consultation with the Lilly clinical research physician.

Hepatic Monitoring Tests

Hepatic Hematology^a

Hemoglobin
Hematocrit
RBC
WBC
Neutrophils
Lymphocytes
Monocytes
Eosinophils
Basophils
Platelets

Haptoglobin^a

Hepatic Coagulation^a
Prothrombin Time
Prothrombin Time, INR

Hepatic Serologies^{a,b}

Hepatitis A antibody, total
Hepatitis A antibody, IgM
Hepatitis B surface antigen
Hepatitis B surface antibody
Hepatitis B Core antibody
Hepatitis C antibody
Hepatitis E antibody, IgG
Hepatitis E antibody, IgM

Hepatic Chemistry^a

Total bilirubin
Direct bilirubin
Alkaline phosphatase
ALT
AST
GGT
CPK

Anti-nuclear antibody^a

Anti-smooth muscle antibody^a

F-Actin Smooth Muscle Antibody IgG^a

Abbreviations: ALT = alanine aminotransferase; AST = aspartate aminotransferase; CPK = creatine phosphokinase; GGT = gamma glutamyl transferase; Ig = immunoglobulin; INR = International Normalised Ratio; RBC = red blood cells; WBC = white blood cells.

a Assayed by local or investigator-designated laboratory.

b Reflex/confirmation dependent on regulatory requirements and/or testing availability.

Attachment 4. Protocol JGDN Pharmacokinetic and Immunogenicity Sampling Schedule

Pharmacokinetic and Immunogenicity Sampling (Parts A and B)

Sample Number	Cycle	Day	Sampling Time	Olaratumab PK ^a	Combination agents PK ^b	Immunogenicity ^c
1	1	1	Prior to olaratumab infusion	X		X
2		8	Within 5 min post olaratumab infusion	X		
3	2	1	Within 15 min prior to olaratumab infusion	X		X
4		1	Within 5 min post chemotherapy infusion	X	X	
5		8	Within 5 min post olaratumab infusion	X		
6	3 and then every other cycle	1	Within 15 min prior to olaratumab infusion	X		X
7	30-day follow-up (Visit 801)	Any time		X		X

Abbreviation: PK = pharmacokinetics.

a A 2.5-mL (~1 mL if patient has <19kg) blood sample will be collected (to generate serum for bioanalysis).

b A 2-mL (~1 mL if patient has <19kg) blood sample will be collected (to generate plasma for bioanalysis).

c A 3.5-mL blood sample will be collected (to generate serum for anti-olaratumab antibody analysis).

Pharmacokinetic and Immunogenicity Sampling (Part C)

Sample Number	Cycle	Day	Sampling Time	Olaratumab PK ^a	Combination agents PK ^b	Immunogenicity ^c
1	1	1	Prior to olaratumab infusion	X		X
2		1	Within 5 min post chemotherapy infusion	X	X	
3		8	Within 5 min post olaratumab infusion	X		
4	2	1	Within 15 min prior to olaratumab infusion	X		X
5		8	Within 5 min post olaratumab infusion	X		
6	3 and then every other cycle	1	Within 15 min prior to olaratumab infusion	X		X
7	30-day follow-up (Visit 801)	Any time		X		X

Abbreviation: PK = pharmacokinetics.

- a A 2.5-mL (~1 mL if patient has <19 kg) blood sample will be collected (to generate serum for bioanalysis).
- b A 2-mL (~1 mL if patient has <19 kg) blood sample will be collected (to generate plasma for bioanalysis).
- c A 3.5-mL blood sample will be collected (to generate serum for anti-olaratumab antibody analysis).

Attachment 5. Protocol JGDN Recommendations for Reporting Serious Adverse Events

Recommendations for Reporting Serious Adverse Events

When contacting Lilly to report a SAE, please have the following information available:

Patient Demographics

- patient identification (number), sex, date of birth, origin, height, and weight

Study Identification

- full trial protocol number, investigator's name, investigator's number

Study Drug

- drug code or drug name, unit dose, total daily dose, frequency, route, start dose, cycle details, start date and last dose date (if applicable)

Adverse Event

- description, date of onset, severity, treatment (including hospitalization), action taken with respect to study drug, clinical significance, test and procedure results (if applicable)

Relationship to Study Drug & Protocol Procedures

Concomitant Drug Therapy

- indication, total daily dose, duration of treatment, start date, action taken

In Case of Death

- cause, autopsy finding (if available), date, relationship to study drug and protocol procedures.

**Attachment 6. Protocol JGDN Creatinine Clearance
Formula**

Protocol JGDN will use the Schwartz formula for the determination of creatinine clearance.

All Females and Pre-adolescent Males:

$$C_{cr} \text{ (mL/min/1.73 m}^2\text{)} = 0.55 \times \text{Height (cm)}/S_{cr} \text{ (mg/dL)}$$

Adolescent Males:

$$C_{cr} \text{ (mL/min/1.73 m}^2\text{)} = 0.70 \times \text{Height (cm)}/S_{cr} \text{ (mg/dL)}$$

Note: C_{cr} = creatinine clearance and S_{cr} = serum creatinine

Source: Schwartz et al. 1976; Schwartz and Gauthier 1985.

